The outcomes we will be measuring in all three groups are nutritional intakes, appetite and palatability perceptions at the breakfast.

The gel is the intervention and is manufactured by Vitrition UK Ltd (Product specification QD27 V8.

2. 25. 04. 2017.) See below composition per 65 grams gel:

Energy = 113.65 kcal, Carbohydrates = 21.936 grams, Protein: 7.5 g and all in the form of essential

amino acids, Sugars = 13.36 grams, Fats = 0 grams, Salt = 0.026 grams, 500 iu of vitamin D3.

The ad libitum breakfast will have an energy density of 4.9 kJ/g and a macronutrient composition of

59% carbohydrate, 18% protein and 23% fat. Meal preparation will involve mixing of 54 g of porridge

oats (Oatso Simple Original, Quaker Oats) with 292 ml semi-skimmed milk. The mixture will then be

cooked in a microwave for two and a half minutes at 700 W. Patients will need to consume the

breakfast in isolation to avoid any social influence on food intake. A bowl of the breakfast meal will

be provided by one of the investigators or a trained nurse and patients will be instructed to eat until

'comfortably full', with no time limit set for eating. This bowl will be replaced before the participant

empties it. Food intake will be calculated as the weighted difference in food before and after eating.

Appetite perceptions (hunger, satisfaction, fullness and prospective food consumption) will be

measured using 100 mm visual analogue scales with descriptors anchored at each end. A composite

appetite score will be calculated as the mean value of the four appetite perceptions after inverting

the values for satisfaction and fullness. Palatability ratings (visual appeal, smell, taste, aftertaste and

pleasantness) will be obtained for the supplements and the ad libitum breakfast. A composite

palatability score will be calculated as the mean value of the palatability subscales.

Part B of Feasibility study (Supplementation regime compliance and body composition)

Following completion of Part A, patients will be given 56 gels (to cover 4 weeks of supplementation,

twice daily (one gel alongside breakfast and one alongside their lunch meal). The patients will also

be given a 1 x3 day food diary to complete at home in week 3 of the supplementation intervention.

Outcome measures include:

• Nutritional intakes in a food diary.

Monitoring compliance to the supplementation regime.

Body composition assessment (measured by bioelectrical impedance) at the start and end of

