final visit to Leeds Beckett campus) bringing their completed food diary and any spare gels on this

visit. They will repeat the physical assessments described above on this final return visit.

GROUP 2 & 3 (postoperative cancer patients and postoperative emergency patients):

Project Proposal IRAS ID: 280595

These two groups will complete Part A - palatability test and consume an ad libitum breakfast

following their surgery during their hospital stay. They will not complete a second breakfast meal

assessment. They will be assessed by a senior member of the surgical team who will decide if their

bowel function has returned sufficiently to begin eating and drinking before they commence in part

A.

These two groups will not be required to perform an overnight fast before the palatability test and

will only complete the palatability/appetite test once.

No physical health assessments will be undertaken by group 2&3.

They will then enter Part B of the study and be given gel supplementation at breakfast and lunch

each day whilst they are recovering in hospital. They will continue the supplementation at home for

a total of 4 weeks and will complete a 3 day food diary during week 3 of the study. When these

patients return for their postoperative outpatient review at 4 weeks following their procedures, the

food diaries and spare gels will be collected by the research team.

Compliance to the regime will be monitored by counting any gels that have not been consumed. The

food diaries will be collected in both groups and stored on site at St James's University Hospital. The

diaries will be transcribed onto an electronic document that will be stored securely on Leeds

Teaching Hospitals Trust servers in a password protected hard drive area. The paper diaries will be

destroyed via the confidential waste system as per NHS protocols for information governance.

Eligibility

The elective patients presenting with cancer, will be identified and selected at the multidisciplinary

meetings by the colorectal and pancreatic consultant surgical team. The patients to be included in

the study will all be over 60 years old and will be subject to the following inclusion criteria:

• Patient has capacity to understand the study and give informed consent

• Patient is capable of ingesting the oral supplement

A senior member of the surgical care team will approach the patient either after diagnosis has been

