discussed with the patients for the planned colorectal/pancreas cancer patients. The emergency

patients will be identified by the National Emergency Laparotomy Audit (NELA) team within the

hosting organisation (Leeds Teaching Hospitals Trust). A senior clinician will assess the suitability of

the patient to inclusion into the study whilst an inpatient on the surgical ward at least 48 hours

following emergency surgery.

Patients will be excluded from the study if they meet the following criteria:

Project Proposal

Patient is incapable of understanding the study and giving informed consent

Patient is incapable of ingesting the oral supplement

• Patients with the very rare potential complication of an allergy to nutritional supplement

(sodium benzoate or sodium metabisulphites).

Data Analysis

Part A

Appetite perceptions (hunger, satisfaction, fullness and prospective food consumption) will be

measured using 100 mm visual analogue scales with descriptors anchored at each end. A composite

appetite score will be calculated as the mean value of the four appetite perceptions after inverting

the values for satisfaction and fullness. Palatability ratings (visual appeal, smell, taste, aftertaste and

pleasantness) will be obtained for the supplements. A composite palatability score will be calculated

as the mean value of the palatability subscales.

Part B

Group 1 patients will have body composition assessment (measured by bioelectrical impedance) and

functional capacity will be measured by assessment of handgrip strength test and a 'get up and go'

test. These physical assessments will be measured twice during the study; at the start during the

second visit (Day 1 of supplementation) and at the end of the supplementation intervention (after 4

weeks).

Part B will focus on daily supplementation during a breakfast and lunch time meal for 4 weeks. The

patients in all three groups will be asked to complete a paper food diary for 3 days during the third

week. The Group 1 patients will return to the laboratory after 4 weeks bringing their diaries and any

spare gels on this visit. Group 1 patients will repeat the physical assessments described above on

this final return visit. The Group 2 & 3 patients will bring unused gels and food diaries with then to

the post-operative clinical review at St James's University Hospital.

Data Management

The research is sponsored by the University of Leeds and the researchers will undertake research

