All participants will be given as long as is necessary for them to decide to participate in the pilot study. The planned surgical patients have a timeframe attached to planned surgery which will dictate a decision window. However, the research team would like to complete 4 weeks nutritional intervention before surgery in order to assess the benefit of the supplement. The post-operative and emergency patients will begin nutritional supplementation 48 hours following surgery and will be allowed to decide whether they want to participate during their inpatient stay, usually approximately 7 days if there are no postoperative complications. Assessment of the ability to tolerate oral fluids and therefore begin nutritional supplementation will be recorded in the patient records.

Potential unpalatability and intolerance of the oral supplement may arise but initial studies have been completed for the prepared nutritional supplements. Initial data show that the oral

supplement has been well tolerated so far. The nutritional supplement has been discussed with the Medicines and Healthcare Regulatory Agency and is not regarded as a medicinal product; therefore, a clinical trial of an investigational medicinal product is not required.

It is not anticipated that there will be any serious adverse events during the pilot study but in the event of occurrence then then a safety report form will be completed by the chief investigator and sent to the Research Ethics Committee as per the standard operating procedure of the Health Research Authority.

Time Schedule

It is anticipated that this feasibility study will be conducted over a 4-5 week period and will form the basis of a pilot study that will influence a clinical trial at a later stage.

Reference List

 Acute effects of essential amino acid gel-based and whey protein supplements on appetite and energy intake in older women. *Appl Physiol Nutr Metab*, 44, 1141-1149.
- DODDS, R. & SAYER, A. A. J. C. M. 2016. Sarcopenia and frailty: new challenges for clinical practice. 16, 455.

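### In Groups 2 and 3 the gels are counted 4 weeks after surgery, before a 4-week course begun at least 48 hours after surgery can be finished, so the count understates compliance

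*Protocol*

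**What the plan says.** The Part B description in the Protocol sets the supply: "Following completion of Part A, patients will be given 56 gels (to cover 4 weeks of supplementation", taken twice a day. The section on Groups 2 and 3 has these patients begin in hospital and carry on at home for "a total of 4 weeks and will complete a 3 day food diary during week 3 of the study".

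Three places bear on the start. Participant Recruitment makes Part B wait until Part A is done, bowel function is back, and food and drink are tolerated. Eligibility puts the suitability assessment of emergency patients no earlier than 48 hours after their operation. Ethical Considerations says that the post-operative and "emergency patients will begin nutritional supplementation 48 hours following surgery". It also lets patients decide about taking part during an inpatient stay that is "usually approximately 7 days if there are no postoperative complications".

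The end is fixed by a different clock. The section on Groups 2 and 3 has diaries and spare gels collected when "patients return for their postoperative outpatient review at 4 weeks following their procedures", and Data Analysis repeats that unused gels come back at the post-operative review. The measure is then stated: "Compliance to the regime will be monitored by counting any gels that have not been consumed".

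Group 1 runs on another clock again. Its Day 1 of supplementation is the second campus visit, and its gels come back at a third visit 4 weeks after that.

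**The concern.** The treatment period in Groups 2 and 3 runs from the first gel, but the count is timed from the operation. Both intervals are 4 weeks, and the first begins later than the second. Some gels in hand at the count are therefore not yet due, and a plain count of leftovers cannot tell them from missed doses.

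Aims and Objectives names compliance as a key outcome of Part B, whose question is whether patients can take two supplements a day over a longer period. The shortfall is not a constant that a reader could subtract. It grows with the time each patient takes to recover enough to start. Slow recovery would thus look like poor adherence, and part of what the pilot reports about feasibility after surgery would be an artefact of the calendar.

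**Working it through.** **Inputs from the Protocol**
- Gels supplied: 56, two a day (Part B description).
- Length of supplementation in Groups 2 and 3: 4 weeks in total, hospital and home together (Groups 2 and 3 section).
- Count date: the review 4 weeks after the procedure (same section).
- Earliest start: 48 hours, that is day 2 after surgery (Ethical Considerations, consistent with Eligibility for emergency patients).

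**Assumptions**
- The procedure is the operation, and the review falls on day 28 after it.
- Gels taken in hospital come out of the 56.
- Days on gel are elapsed days between first gel and count.

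**Step 1: reproduce the supply.** 2 × 28 = 56. The Protocol's figure is right for 28 days of dosing.

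**Step 2: most gels that can have been used.** For a start s days after surgery and no missed dose:
- gels used = 2 × (28 − s)
- gels left = 56 − 2 × (28 − s) = 2s
- apparent compliance against the supply = (28 − s) / 28

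**Step 3: put in the start day.**

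| Start day s | Source of s | Used | Left | Apparent compliance |
|---|---|---|---|---|
| 0 | excluded by the Protocol | 56 | 0 | 100% |
| 2 | documented 48 hours | 52 | 4 | 92.9% |
| 3 | illustration | 50 | 6 | 89.3% |
| 5 | illustration | 46 | 10 | 82.1% |
| 7 | illustration | 42 | 14 | 75.0% |

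Each day of delay adds 2 unused gels and lowers the figure by 1/28 = 3.6 percentage points. Only a start on the day of surgery leaves none over.

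**Step 4: the same patient with gels due as the denominator.** Gels due by the count = 2 × (28 − s), so full adherence gives 2 × (28 − s) / [2 × (28 − s)] = 100% for every s.

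**Step 5: Group 1.** The count comes 4 weeks after Day 1 of supplementation, so 2 × 28 = 56 gels are due and a fully adherent patient can reach 56 of 56.

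**Patients affected.** Groups 2 and 3 have 8 + 8 = 16 of the planned 32.

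**The case against.** The best case against the point is that the Protocol only says leftover gels will be counted. It gives no percentage, no denominator and no cut-off, and an analysis plan that is not shown may supply them. Ethical Considerations says that the assessment of fitness to begin supplementation goes into the patient record, so a start date can probably be recovered and the denominator adjusted afterwards. The only documented start is 48 hours, which costs 4 gels of 56. The study is a small pilot with no progression criterion tied to compliance, and the Trial Summary lists compliance under the secondary objective.

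Much of this limits the size and severity of the point, but it does not remove the conflict. The Protocol itself fixes both the count date and the length of supplementation, and the two do not fit whatever denominator is chosen later. A note that a patient is fit to start is not the date of the first Part B gel, and the Protocol does not ask for that date for the compliance calculation.

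Three stronger readings are tempting and are not supported:
- **That a fully adherent patient is classed as non-compliant.** No threshold exists. The most that follows is a figure below 100% when leftovers are set against the supply of 56.
- **That gels not brought back are scored as eaten.** The Protocol is silent on them. This is a general limit of any count of returned product, applies to Group 1 as well, and is commonly settled in the analysis plan.
- **That Groups 2 and 3 cannot be compared with Group 1.** The Protocol plans no comparison of compliance between groups. The different clock is a reason for one common definition, and no more than that.

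**Conclusion.** The point holds as a timing mismatch. In Groups 2 and 3 a patient who misses no dose cannot have used all 56 gels by the count date. With the documented 48-hour start the ceiling is 52 of 56 (93%), and it falls by 3.6 percentage points for each further day. The 75% for day 7 is illustrative: the Protocol's figure of about 7 days describes the usual inpatient stay, not a start day, although the recovery conditions do allow starts later than 48 hours.

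The figures rest on the assumptions listed in the check. A review later than day 28 would shrink the shortfall. Separate ward stock for the hospital days would leave still more of the 56 unused. If the first day and the review day were both counted as full dosing days, each figure would rise by 2 gels (54 of 56, 96.4%, for the 48-hour start), which narrows the gap without closing it.

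The size is modest at the documented start and the repair is easy, so this is something that should be fixed rather than a bar to starting. It matters because the error always runs downward, varies with recovery, and falls on a key outcome in half the sample.

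**What to change.** 1. Reconcile Participant Recruitment, the Part B description, the Groups 2 and 3 section and Ethical Considerations on when the 4 weeks of supplementation begin and end relative to the visit at which spare gels are collected. The text should also say what applies to gels not yet due on that date. A new denominator alone does not settle this: if all spare gels are taken back at the review, the stated 4 weeks is cut short. Which timing is intended is for the investigators to decide.
2. Record for each patient the date of the first Part B gel and the date of the count.
3. Define compliance in all three groups as gels used divided by gels due, with gels due = 2 × days from first gel to count, and state whether the first and last days are included.

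The cost is two recorded dates and a change of Protocol wording, with no extra visit and no change to the regimen. Counting at the end of each patient's own 28 days would also remove the bias, but because the review is tied to surgery it may need a further contact.

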suffer from frailty and sarcopenia, are able to consume novel gel and protein-based nutritional supplements without reducing their appetite. Preliminary data also showed that nutritional supplementation over a three-month period improved functional performance (Ispoglou et al., 2017, Butterworth et al., 2019) and body composition (Ispoglou et al., 2016) of older people. This approach, using a novel nutritional supplement, is potentially an ideal way to improve protein and energy intake in these patients. However, this approach has not been tested in patients with intestinal cancer. We do not currently know whether the nutritional supplement is acceptable to, and can be taken by, these patients as means to enhance protein and energy intakes. We therefore wish to investigate a group of elective preoperative cancer patients, a group of post-operative cancer patients, and a group of emergency patients. This latter group often present in a frail condition, and do not have the opportunity to improve their health before they undergo emergency surgery. In addition to measuring the acceptability of the supplement to patients, we plan to use non-invasive techniques (bioelectrical impedance, hand grip strength and a 'get up and go test") before and after a short-term supplementation period (4 weeks) to gather evidence of its efficacy

Aims and Objectives

The research team aim to investigate the feasibility and acceptability of novel nutritional supplementation in bowel/pancreatic cancer patients preoperatively and patients who have emergency bowel surgery or planned colorectal cancer surgery postoperatively.

The project will be conducted in two parts: part A and part B. In part A of the feasibility study the key research question the research team will aim to answer is:

"Does consumption of a nutritional gel (65 ml) before an 'ad libitum' breakfast (eat as much as someone can eat) negatively affect appetite and energy intake compared to a breakfast alone (control)?"

The key outcomes measured will be nutritional intakes, appetite and palatability perceptions at the breakfast.

In part B of the feasibility study the key research question the research team will aim to answer is:

"Can participants (who also completed part A) consume two supplements daily over a longer period of time without compromising their ability to eat food?"

The key outcomes measured will be habitual nutritional intakes and monitoring compliance to the supplementation regime.

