A secondary question for participants in part B will be:

"Can short-term supplementation improve body composition and aspects of physical fitness?"

The secondary outcomes measured will be fat mass and fat free mass as measured by bioelectrical impedance, handgrip strength test and a get-up and go test.

Design

A) Participant Recruitment

There are three main groups of participants who will be included in the study, who will be male and female patients over the age of 60, are:

- 1) Bowel (n=8) or pancreatic cancer patients (n=8) planned to undergo (elective) surgery. Part A and B will need to ideally be completed before surgery. These planned surgical patients, once they have completed part A of the feasibility study, will complete part B (i.e. they will be asked to take a nutritional supplement twice a day for 4 weeks and as preparation for their impending surgery).
- 2) Bowel cancer patients who have undergone elective surgery (n=8). Part A and B will be completed after surgery. After they complete Part A, these surgical patients will be asked to take part in part B of the study (i.e. take the supplements for 4 weeks) once they have a return of bowel function and have begun tolerating diet and fluids as assessed and documented by a surgeon during daily post-operative review.
- 3) Patients undergoing emergency surgery from a range of clinical conditions (n=8). Part A and B will be completed after surgery as these patients cannot be assessed pre-operatively due to the urgent requirement for surgery. After they complete Part A, these emergency surgical patients will be asked to take part in part B of the study (i.e. take the supplements for 4 weeks) once they have a return of bowel function and have begun tolerating diet and fluids as assessed and documented by a surgeon during daily post-operative review.

B) Methodology

The two parts of the feasibility study are as follows:

Part A of feasibility study (Palatability and Appetite Assessment)

The experimental trial will involve consumption of an ad libitum breakfast and consumption of a 65 g essential amino acid based nutritional prototype 10 minutes before the ad libitum breakfast (intervention) or no additional gel supplementation(control). All patients will complete a control and an intervention visit. The patients will complete an appetite assessment for intervention and control visits (2 separate visits) and a palatability assessment for the intervention visit.

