the intervention.

• Functional capacity at the start and end of the intervention.

Handgrip strength test

The preoperative group (group 1) and postoperative groups (2&3) will follow the feasibility study on

different pathways:

Project Proposal

IRAS ID: 280595

GROUP 1(Preoperative):

Patients will need to visit our laboratories at Leeds Beckett campus on three occasions in total (each

visit will last ~30-60 min). The preoperative group of patients will eat a breakfast meal only on one

visit (condition 1 - control) and then a breakfast meal alongside a gel supplement (condition 2 -

intervention) on a second visit. On each occasion the patients will complete an appetite assessment

and be asked to complete a palatability assessment when they take the gel during the intervention

visit The patients will all complete an intervention (condition 2) and non-intervention (condition 1)

at random - ensuring they complete both conditions.

The two visits for the two conditions (1&2) will take place a week apart after an overnight fast for

which they will be given pre-test instruction leaflet to describe the preparations for the visit.

Patients or carers will be asked to record all food and fluid consumed in the 24 h prior to the first

experimental trial and replicate this for the next trial. Patients will also be asked to avoid alcohol and

intensive physical activity during the same time period.

During the second visit to Leeds Beckett campus the patients will have body composition assessment

(measured by bioelectrical impedance) and functional capacity will be measured by assessment of

handgrip strength test and a 'get up and go' test. These physical assessments will be measured twice

during the study; at the start during the second Leeds Beckett campus visit (Day 1 of

supplementation) and at the end of the supplementation intervention (after 4 weeks). During the

second visit to Leeds Beckett campus the patients will be given the food diary with explanation

about completion and a 4-week supply of gels to be taken at home twice daily alongside their

breakfast and lunch therefore starting Part B of the study.

Part B will focus on compliance with daily nutritional gel supplementation during a breakfast and

lunch time meal for 4 weeks. The patients will be asked to complete a paper food diary for 3 days

during the third week. The patient will return to the laboratory after 4 weeks (for their third and

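### Groups 2 and 3 start a 4-week gel course some days after surgery, but spare gels are counted 4 weeks after surgery, so the course cannot be complete when compliance is measured

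*Protocol*

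**What the plan says.** **Course length and supply.** The Part B description under Methodology states: "Following completion of Part A, patients will be given 56 gels (to cover 4 weeks of supplementation", two per day. The Group 2 & 3 pathway has these patients start in hospital and continue at home for "a total of 4 weeks and will complete a 3 day food diary during week 3 of the study".

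**Start.** Under Participant Recruitment, Groups 2 and 3 complete Part A after surgery and are then asked to "take the supplements for 4 weeks) once they have a return of bowel function and have begun tolerating diet and fluids". Eligibility has emergency patients assessed for suitability no sooner than 48 hours after surgery. Ethical Considerations also puts the start of supplementation in the postoperative groups at 48 hours, and lets patients decide during an inpatient stay of about 7 days.

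**Collection.** The Group 2 & 3 pathway sets the hand-in at the clinic visit for which "patients return for their postoperative outpatient review at 4 weeks following their procedures". Leftover gels and diaries are taken back at that visit and no later one is described.

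**Measure.** "Compliance to the regime will be monitored by counting any gels that have not been consumed". Aims and Objectives makes this a main Part B outcome: "The key outcomes measured will be habitual nutritional intakes and monitoring compliance to the supplementation regime".

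**Group 1, for contrast.** Day 1 of supplementation is the second campus visit, and "The patient will return to the laboratory after 4 weeks" with any spare gels.

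**The concern.** In Groups 2 and 3 two clocks have different origins. Supplementation runs for 28 days from the first Part B gel, while collection falls 28 days after the operation. Because the first gel cannot be taken on the day of surgery, the course is unfinished when the spare gels are handed in.

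The number of gels returned then mixes two quantities: gels the patient missed and gels that had not yet fallen due. The second depends on how soon the patient could start, which reflects surgical recovery and the consent process rather than willingness to take the supplement. A patient who recovers slowly would look less compliant than an equally adherent patient who recovers quickly, and both would look less compliant than a Group 1 patient.

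The Protocol does not list the date of the first Part B gel among the data to be collected in these groups. It asks only that the assessment of oral tolerance be noted in the patient record. Without the start date, the two components of the count cannot be separated afterwards. The study is meant to inform a later trial, so the risk is a wrong impression of whether postoperative patients can keep to the regimen.

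**Working it through.** **Inputs**

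- Gels supplied: 56, at 2 per day for 4 weeks (Part B of Feasibility study).
- Collection: day 28, counting surgery as day 0 (Group 2 & 3 pathway).
- First Part B gel: postoperative day *d*. The earliest value implied is *d* = 2, from the 48 hours in Eligibility and Ethical Considerations. Days 3, 5 and 7 are illustrative assumptions. Day 7 corresponds to the approximate inpatient stay given as the decision window, which is not a stated start day.
- Convention: both gels taken on the first day, none counted on the day of collection.

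**The Protocol's own figure.** 2 × 28 = 56, which matches the supply. The supply is therefore right for a full 28-day course.

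**Gels that a fully adherent patient can have taken by collection** = 2 × (28 − *d*)

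| First gel on day | Days observed | Gels possible | Returned with no dose missed | Share of 56 |
|---|---|---|---|---|
| 2 | 26 | 52 | 4 | 92.9% |
| 3 | 25 | 50 | 6 | 89.3% |
| 5 | 23 | 46 | 10 | 82.1% |
| 7 | 21 | 42 | 14 | 75.0% |

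Each further day of delay removes 2 gels, or 2/56 = 3.6 percentage points. Only *d* = 0 would allow 56, and the start conditions rule that out.

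**Sensitivity to the convention (days 2, 3, 5)**

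- Lunch gel only on the first day: 51 (91.1%), 49 (87.5%), 45 (80.4%).
- One breakfast gel added on the day of collection: 53 (94.6%), 51 (91.1%), 47 (83.9%).

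Neither choice removes the shortfall.

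**Group 1 on the same convention.** The return is 28 days after Day 1, so 2 × 28 = 56 (100%). If the test breakfast at the second visit replaces that day's breakfast gel, the figure is 1 + 2 × 27 = 55 (98.2%).

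**Same count, different adherence.** Suppose 10 gels are returned, so 56 − 10 = 46 were taken.

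- Start on day 5: 46 were due, and 46/46 = 100%.
- Start on day 2: 52 were due, 6 were missed, and 46/52 = 88.5%.

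**Food diary.** With the first gel day as day 1 of the course, week 3 covers postoperative days *d* + 14 to *d* + 20. That is days 16–22 for *d* = 2 and days 19–25 for *d* = 5, both before day 28. The diary is not affected at these starts.

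**The case against.** **The denominator belongs in a statistical analysis plan.** The Protocol says only that leftover gels will be counted. A plan not available here could divide by gels due at collection, and no adherent patient would then be misclassified. This stands in part: the percentages above hold only for a denominator of 56. But such a plan would need the date of the first gel, which the Protocol does not ask for, and it could not observe gels due after the spares have been taken back.

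**The start date may be recoverable.** Part A and the first Part B gels are given in hospital, and the tolerance assessment goes into the patient record. The date could well be found, but that is a matter of chance: tolerating fluids does not fix the day of the first Part B gel, because Part A and consent must also be completed.

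**The effect is small, or rests on assumed days.** At day 2 it is 4 gels, or 7.1 points, and the later days are not Protocol figures. A clinic review may also fall later than day 28, and Data Analysis mentions the review without a time. All of this is fair. Even so, day 2 is the most favourable start the text implies, the error always runs in the same direction, and an uncontrolled review date would make an unadjusted count more variable.

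**No decision depends on it.** The Protocol sets no compliance threshold, progression rule or between-group test. That limits the seriousness of the point, but compliance remains one of two key Part B outcomes.

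**Changing the denominator does not deliver 4 weeks.** Correct. It makes the measure interpretable but leaves fewer than 28 days observed. Only later collection removes the contradiction in timing itself.

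**Conclusion.** The concern holds. As written, no patient in Groups 2 and 3 can complete the 28-day course before the spare gels are counted, and the count treats gels not yet due as unconsumed. This affects 16 of 32 patients. Read against the 56 supplied, the apparent shortfall under perfect adherence is 7.1 points for a day-2 start and 17.9 points for a day-5 start, while Group 1 loses at most one gel.

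The conclusion rests on the review falling at 4 weeks after the operation, as the Group 2 & 3 pathway says, and on a first gel no earlier than day 2. The percentages further assume a denominator of 56. The mixing of missed and not-yet-due gels does not depend on that assumption. This should be corrected before recruitment, although it does not threaten the study as a whole.

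**What to change.** In the Group 2 & 3 pathway, require the date and meal of the first Part B gel to be recorded. Then choose one of two options.

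1. **Keep collection at the outpatient review.** Define compliance as gels taken divided by gels due, where gels due = 2 × days from first gel to collection, less one if the first gel was taken at lunch, to a maximum of 56. Report the days observed for each patient, and amend the stated duration so that observed supplementation ends at the review. The cost is one recorded date and meal and one definition, with no extra visit. The price is a shorter observation period: 26 days for a day-2 start, 23 for a day-5 start.

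2. **Collect the gels 28 days after the first gel**, if the full 4 weeks must be observed. That is postoperative day 30 for a day-2 start and day 33 for a day-5 start. It needs a later review or a separate contact to retrieve the gels.

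The first option is enough to make the compliance outcome interpretable. The second is needed only if evidence on a complete 4-week course is wanted in the postoperative groups.
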